## 6.9 PRIOR AND CONCOMITANT THERAPY

### 6.9.1 General Guidelines

All prior treatments received by the patient within 30 days of the initial Screening visit will be recorded on the patient's eCRF including the treatment's name, indication and the start and stop dates.

Any medications (including prescription, over-the-counter, herbal and food supplements and health store products) to be taken during the study must be approved by the Investigator.

All approved concomitant medications taken by the patient must be recorded on the eCRF, along with the indication and start and stop dates, dose and dose frequency.

### 6.9.2 Disallowed Previous Medications/Therapies

The following medications are not permitted prior to the Screening visit:

- Any r-hGH therapy.
- Systemic corticosteroids other than in replacement doses within the 3 months before ICF signing (temporary adjustment of glucocorticoids, as appropriate, is acceptable).
- Anabolic steroids other than gonadal steroid replacement therapy within 2 months before study entry.
- Use of IP (within 30 days of ICF signing).

### 6.9.3 Allowed Medications

The only concomitant medications allowed to be used in this study are those used at Baseline to control existing medical condition and/or those taken during the study to treat AEs. All concomitant medications used to treat AEs will be recorded in the patient's medical file and on the appropriate eCRF page.

Careful monitoring is advisable when MOD-4023 is administered in combination with other drugs known to be metabolized by CYP450 liver enzymes. However, formal drug interaction studies have not been conducted. In patients with diabetes mellitus requiring drug therapy, the dose of insulin and/or oral/injectable agent may require adjustment when MOD-4023 treatment is initiated.

#### 6.9.4 Prohibited Concomitant Medication

The following medications are not permitted during the study and may lead to withdrawal of the patient from the study:

- Any hormonally active medication other than replacement therapy for pituitary failure. Glucocorticoid replacement dosing should be carefully adjusted in children receiving MOD-4023 and Genotropin® and glucocorticoid treatments to avoid both hypoadrenalism and an inhibitory effect on growth.
- Any new long-term glucocorticoid treatment should be noted on the concomitant medication form and the patient should be retained in the safety population, but not the per-protocol population. Short term glucocorticoid treatment is allowed.
- Anabolic steroids (including testosterone replacement therapy) should not be taken.
- Weight loss drugs.
- Psychiatric medications typically associated with weight changes and/or diabetes excluding medications used to treat ADHD.

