	
chronically a dose greater than 400 µg/day of inhaled budesonide or equivalent as provided in Appendix J.
 
 
12. Major medical conditions and/or presence of contraindication to r-hGH treatment.
 
13. More than 1 closed epiphyses.
 
14. Known or suspected Human Immunodeficiency Virus (HIV)-positive patient, or patient with advanced diseases such as Acquired Immunodeficiency Syndrome (AIDS) or tuberculosis.
 
15. Drug, substance, or alcohol abuse.
 
16. Known hypersensitivity to the components of study medication.
 
17. Other causes of short stature such as celiac disease, uncontrolled primary hypothyroidism and rickets.
 
18. The patient and/or the parent/legal guardian are likely to be non-compliant in respect to study conduct.
 
19. Participation in any other study of an investigational agent within 30 days prior to ICF signature (including administration of investigational agent).
 
20. Study enrollment requirements have been met or the study has been closed by the Sponsor prior to the completion of screening process.
 
 
Exclusion during the LT-OLE:
 
 
21. Concomitant administration of other treatments that may have an effect on growth such as anabolic steroids, or sex steroids (other than for hormonal replacement), with the exception of ADHD drugs or hormone replacement therapies (thyroxin, hydrocortisone, testosterone, estrogen/progesterone, desmopressin [DDAVP®])
 
22. Change in medical condition during the treatment period (such as, but not limited to, development of a serious inter-current critical illness, a severe adverse drug reaction, etc.)
 
23. Positive pregnancy test.
 
24. Unresolved drug related (MOD-4023 or Genotropin®) SAE from the treatment period as per MM judgement.
 

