**3. STUDY DESIGN**

The study will consist of 12 months, open-label, multi-center, randomized, active controlled, parallel group study comparing efficacy and safety of weekly MOD-4023 to daily GH, Genotropin®.

Both drugs will be injected using a PEN device.

The study will be divided into two parts:

**Main Study Period (main study):** After an 8 wk screening perioda, patients meeting the eligibility criteria, as approved by global study MM, will be randomized in a 1:1 ratio to weekly SC doses of MOD-4023 (investigational treatment) or daily SC administration of Genotropin® (reference therapy) for 12 months. The key safety data will be reviewed by an independent DSMB every 4 months or on an *ad hoc* basis.

**LT-OLE Period (LT-OLE):** Patients who received MOD-4023 during the main study will continue in the LT-OLE with the same dose (mg/kg/wk) of MOD-4023. Patients who received Genotropin® during the main study will be switched to MOD-4023 and will begin treatment with a dose of 0.66 mg/kg/wk beginning no less than one day after cessation of Genotropin® treatment. The key safety data will be reviewed by an independent DSMB approximately every 6 months.

During the entire study (main study and LT-OLE), the dose of MOD-4023 and Genotropin® will be adjusted every 3 months based on the patient's body weight. Doses may be decreased for safety reasons according to the pre-defined dose-adjustment criteria (which will be based on the severity

a If the patient's screening process is delayed because of a benign illness or unforeseen benign condition (i.e. pharyngitis, viral GI problems, minor accident or trauma, etc.) or other technical issue that is related screening procedures (for example, delays with laboratory results) extra time will be added to the duration of the screening period, but not in excess of an additional four wks (total of 12 wks screening period).

of AEs or repeated, elevated levels of IGF-1). The dose will be decreased based on two, repeated day 4(-1) post-dose levels of IGF-1 SDS  $\geq +2.0$  (Section 6.4). During the LT-OLE, dose reduction for IGF-1 level  $>+2.0$  SDS will be made following consultation with the Global Study MM on an individual patient basis

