#### **4.2 EXCLUSION CRITERIA**

1. Children with prior history of leukemia, lymphoma, sarcoma or any other form of cancer.
2. History of radiation therapy or chemotherapy.
3. Malnourished children defined as BMI <-2 SDS for age and sex.
4. Children with psychosocial dwarfism.
5. Children born small for gestational age (SGA – birth weight and/or birth length <-2 SDS for gestational age).
6. Presence of anti-hGH Ab at screening.
7. Any CS abnormality likely to affect growth or the ability to evaluate growth, such as, but not limited to, chronic diseases like renal insufficiency, spinal cord irradiation, etc.
8. T2 and T1 diabetic patients, who in the opinion of the investigator are not receiving standard of care treatment or are non-compliant with their prescribed treatment or who are in poor metabolic control. Criteria for controlled diabetes are defined in [Appendix F](#).
9. Chromosomal abnormalities including Turner's syndrome, Laron syndrome, Noonan syndrome, Prader-Willi syndrome, Russell-Silver syndrome, SHOX mutations/deletions and skeletal dysplasias.
10. Concomitant administration of other treatments that may have an effect on growth such as anabolic steroids, or sex steroids, with the exception of ADHD drugs or hormone replacement therapies (thyroxin, hydrocortisone, desmopressin [DDAVP®]).
11. Children requiring glucocorticoid therapy (e.g. for asthma) that are taking chronically a dose greater than 400 µg/day of inhaled budesonide or equivalent as described in [Appendix J](#).
12. Major medical conditions and/or presence of contraindication to r-hGH treatment.
13. More than 1 closed epiphyses.
14. Known or suspected HIV-positive patient, or patient with advanced diseases such as AIDS or tuberculosis.
15. Drug, substance, or alcohol abuse.

Effective Date: Date of final electronic approval

16. Known hypersensitivity to the components of study medication.
17. Other causes of short stature such as celiac disease, uncontrolled primary hypothyroidism and rickets.
18. The patient and/or the parent/legal guardian are likely to be non-compliant in respect to study conduct.
19. Participation in any other study of an investigational agent within 30 days prior to ICF signature (including administration of investigational agent).
20. Study enrollment requirements have been met or the study has been closed by the Sponsor prior to the completion of screening process.

Exclusion during the LT-OLE:

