21. Concomitant administration of other treatments that may have an effect on growth such as anabolic steroids, or sex steroids (other than for hormonal replacement), with the exception of ADHD drugs or hormone replacement therapies (thyroxin, hydrocortisone, testosterone, estrogen/progesterone, desmopressin [DDAVP®])
22. Change in medical condition during the treatment period (such as, but not limited to, development of a serious inter-current critical illness, a severe adverse drug reaction, etc.)
23. Positive pregnancy test.
24. Unresolved drug related (MOD-4023 or Genotropin®) SAE from the treatment period as per MM judgement.

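### Section 6.9.4 bars testosterone replacement with no period limit, while LT-OLE criterion 21 exempts it; the ban was probably meant for the main study, but nothing in the protocol says so

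*Protocol*

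**What the plan says.** Protocol Section 6.9.4 opens its list with "The following medications are not permitted during the study and may lead to withdrawal of the patient from the study". The first bullet covers "Any hormonally active medication other than replacement therapy for pituitary failure", so replacement for pituitary failure is exempt there. The third bullet then reads "Anabolic steroids (including testosterone replacement therapy) should not be taken". Neither the section heading, the lead-in nor the bullet is limited to one part of the trial.

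The eligibility rules differ by period. Main-study criterion 10 (Section 4.2) excludes treatments affecting growth, including anabolic and sex steroids, "with the exception of ADHD drugs or hormone replacement therapies (thyroxin, hydrocortisone, desmopressin"; testosterone is not among the exemptions. LT-OLE criterion 21 excludes sex steroids with a carve-out. The Synopsis wording is "sex steroids (other than for hormonal replacement", and Section 4.2 lists the exempt treatments as "hormone replacement therapies (thyroxin, hydrocortisone, testosterone, estrogen/progesterone, desmopressin" together with ADHD drugs.

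Three other sections bear on the point:

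- Section 4.4 lists use of a prohibited medication among its general reasons for discontinuation, subject to consulting the medical monitor. That list comes before a separate set of LT-OLE reasons.
- Section 6.9.1 requires investigator approval of any medication taken.
- Section 6.9.3 allows only medications in use at Baseline for an existing condition and those given to treat adverse events.

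**The concern.** Inclusion criterion 1 admits children whose growth hormone insufficiency is part of multiple pituitary hormone deficiency, and Section 1.1 itself notes delayed puberty and genital underdevelopment in this disease. Boys may remain in the LT-OLE up to a bone age of 16 years, unless growth slows to the Section 4.4 limit or another exit rule applies. A boy who needs testosterone replacement while in the extension is therefore foreseeable.

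For that boy the protocol gives two answers. Criterion 21 lets him stay on replacement; 6.9.4, taken at its word, forbids the drug and opens the way to withdrawal. The trial runs at about 200 sites in 30 to 40 countries, so different sites could treat, withhold treatment, log a deviation, or refer the child for withdrawal. What is at stake is the care of individual children and consistent conduct of the extension.

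**Working it through.** No arithmetic applies. The check compares the relevant texts and asks whether any of them fixes the scope of the ban.

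**1. Do the two rules conflict on their face?**

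| Rule | Period stated | Testosterone replacement |
|---|---|---|
| Criterion 10 (4.2) | Main study | Not among the exemptions |
| Criterion 21 (4.2 and Synopsis) | LT-OLE | Exempt by name |
| 6.9.4, first bullet | None | Exempt if it is replacement for pituitary failure |
| 6.9.4, third bullet | None | Prohibited by name |

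If the third bullet applies in the LT-OLE, it contradicts criterion 21. For a boy with pituitary hypogonadism it also sits awkwardly with the first bullet of its own list. If it applies only in the main study, it agrees with criterion 10 and the conflict with criterion 21 disappears. Everything turns on scope.

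**2. Does the protocol's use of *the study* fix the scope?** It does not; usage is mixed.

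- Broad sense: Section 3 divides the study into two parts and writes "During the entire study (main study and LT-OLE") when setting out dose adjustment.
- Narrow sense: Section 3 opens by describing the study as the 12-month randomized comparison, and Section 5.11 places the end of the study at Visit 8, after 12 months of treatment.
- Elsewhere the drafters often name the period when they mean one, for example blinding in Section 6.6 (main study) and the individual dose-reduction decisions in Section 6.4.1 (LT-OLE). Section 6.9.4 does not.

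**3. Does the content of 6.9.4 indicate intent?** Yes, but only by inference. The first bullet speaks of children receiving Genotropin, which is given only in the main study. The second removes patients from the per-protocol population, which SAP Section 4 marks as not applicable in the extension. Together with the match to criterion 10, this points to the main study.

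**4. Does any other section settle it?** None does.

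- Section 6.9.2 carries its own carve-out ("Anabolic steroids other than gonadal steroid replacement therapy within 2 months before study entry"), but it governs use before entry and is silent on the LT-OLE.
- Section 4.4 attaches possible discontinuation to prohibited medication without a period limit.
- The SAP only lists concomitant medications (6.4.4) and sets no restriction.

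**5. Does 6.9.3 give a separate route?** Only in part. Replacement started during the LT-OLE fits 6.9.3 if it treats an adverse event. A clinically significant laboratory finding can count as one (Sections 7.1 and 8.6.8). However, Section 7.1 counts disease-related events only when they worsen beyond expected progression, so hypogonadism expected from known pituitary disease may not qualify. This gap is not specific to boys: it also reaches newly started estrogen or progesterone in girls, which criterion 21 likewise exempts.

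**The case against.** The strongest reply is that a sensible reader would resolve this correctly. Criterion 21 is specific to the LT-OLE and names testosterone, so it should prevail over a general list. The first bullet of 6.9.4 already protects replacement for pituitary failure. Withdrawal is only possible, not mandatory, and goes through the medical monitor; the investigator approves each medication. What remains, on this view, is editorial.

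Much of that stands. The main-study reading is the likelier one, and these safeguards make a bad outcome less probable. But they are discretionary steps that do not state which rule governs. The specific-over-general argument also runs both ways: within 6.9.4 it is the testosterone bullet that is specific, against the general exemption two bullets above it.

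A reader might go further than the documents allow in three ways:

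- *That the protocol defines the study to include the LT-OLE, so the ban plainly applies there.* The mixed usage in Sections 3 and 5.11 does not support this.
- *That the problem can be sized from the age at which boys enter the extension, or from the testosterone assays scheduled from age 13.* That age is a laboratory sampling threshold; no passage makes it a trigger for treatment.
- *That the whole matter is confined to boys.* The testosterone bullet is, but the 6.9.3 gap is not.

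**Conclusion.** The inconsistency is real and should be corrected. An operative rule, followed literally, gives the wrong result for a boy needing testosterone replacement in the extension, and no passage tells a site to disregard it. The conclusion rests on the absence of any period limit in 6.9.4 and on the explicit exemption in criterion 21. The view that the ban was meant for the main study is an inference, though a well-supported one. It would be wrong to infer that the sponsor intended to deny replacement in the extension.

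The size is modest. The documents do not say how many boys would be affected, and no estimate is offered. The conflict with criterion 21 arises only in the LT-OLE, which is analysed descriptively without hypothesis tests (Protocol 8.5; SAP 5.1). The 12-month non-inferiority comparison and its sample size are untouched.

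**What to change.** In Section 6.9.4, either limit the testosterone bullet to the main study or append: *except gonadal hormone replacement during the LT-OLE, per criterion 21*.

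As a secondary conforming edit, add to the permitted medications in Section 6.9.3: *and hormone replacement permitted by criterion 21 during the LT-OLE*. This also covers newly started estrogen or progesterone in girls.

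Section 4.4 needs no change, because replacement would no longer be a prohibited medication in the extension. No analysis flag is needed. The cost is one clause in each section at the next amendment, with no new procedures, data or tables.

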## 7. SAFETY AND PHARMACOVIGILANCE

### 7.1 ADVERSE EVENT

An AE is any adverse change from the patient baseline condition, whether or not considered IP related. This includes any subjective signs, symptoms or diagnosis, clinical significant deviation from baseline laboratory values or vital signs, or worsening (more severe, more frequent or increased in duration during the IP treatment) of the concomitant disease present at baseline visit (after initiation of IP treatment). Stable chronic conditions that are present prior to study entry and do not worsen during the study will not be considered AEs. Disease-related AEs will be considered AEs only if they worsen beyond what would be expected in the normal progression of the disease. In all cases, the etiology should, as much as possible, be identified and the Sponsor notified.

An abnormal result of diagnostic procedures including abnormal laboratory or vital sign findings will be considered an AE if it:

- Results in patient's withdrawal by the investigator,
- Is associated with clinical signs or symptoms,
- Is considered by the physician to be of CS.

AEs reported by the patient or observed by the Investigator will be individually listed on an AE form in the eCRF as follows: the specific event or condition, whether the event was present pre-study, the dates and times of occurrence, duration, severity, relationship to study medication, specific counter measures and outcome.

The intensity or severity of the AE will be characterized as:

- Mild: Transient or mild discomfort; no limitation in activity; no medical intervention/therapy required.
- Moderate: Mild to moderate limitation in activity - some assistance may be needed; no or minimal medical intervention/therapy required.
- Severe: Marked limitation in activity, some assistance usually required; medical intervention/therapy required; hospitalization possible.

Effective Date: Date of final electronic approval

The investigator will document in his/her opinion the relationship of the AE to study treatment using the criteria outlined in Table 1.

**Table 1: AE Relationship Criteria**

Relationship	Criteria
Not related	
 
The temporal sequence of the AE onset relative to administration of the IP is not reasonable.
 
Disease or other drugs provide plausible explanations.
 
Dechallenge (if performed) is negative or ambiguous.
 

Unlikely related	
 
The temporal sequence of the AE onset relative to the administration of the IP is reasonable.
 
Could also be explained by disease or other drugs.
 
Dechallenge (if performed) is positive or uncertain.
 
Rechallenge is negative.
 

Possibly related	
 
The temporal sequence of the AE onset relative to administration of the investigational is reasonable.
 
Unlikely to be attributed to disease or other drugs.
 
Dechallenge (if performed) is positive.
 

Related	
 
The temporal sequence of the AE onset relative to administration of the IP is reasonable.
 
Cannot be explained by disease or other drugs.
 
Dechallenge (if performed) is positive and pharmacologically/ pathologically plausible.
 
Rechallenge (if feasible) is positive.
 
The AE shows a pattern consistent with previous knowledge of the IP or product class, i.e., pharmacologically or phenomenologically recognized/plausible or an objective and specific medical disorder.
 

## 7.2 SERIOUS ADVERSE EVENT

A SAE is any AE occurring at any dose that suggests a significant hazard or side effect, regardless of the investigator or Sponsor's opinion on the relationship to the IP and that results in, but may not be limited to, any of the following outcomes:

- death (regardless of the cause),
- a life-threatening adverse drug experience,
- inpatient hospitalization or prolongation of existing hospitalization (any inpatient hospital admission that includes a minimum of an overnight stay in a health care facility),
- a persistent or significant disability/incapacity,
- a congenital anomaly or birth defect.

Important medical events that may not result in death, be life-threatening, or require hospitalization may be **serious** when, based upon appropriate medical judgment, they may jeopardize the patient and may require medical or surgical intervention to prevent one of the outcomes listed above.

Hospitalization for elective treatment of a pre-study condition that did not worsen while on study and hospitalizations for treatment of non-AEs (e.g. cosmetic surgery or diagnostic procedure) are not considered SAEs.

**Significant medical events** are those which may not be immediately life-threatening, but may jeopardize the patient and may require intervention to prevent one of the other serious outcomes listed above. Examples of such events are intensive treatment in an emergency room or at home for allergic bronchospasm; blood dyscrasias or convulsions that do not result in hospitalization; resulting in an AE will normally be considered serious by this criterion.

Inpatient hospitalization or prolongation of existing hospitalization means that hospital inpatient admission and/or prolongation of hospital stay were required for treatment of AE, or that they occurred as a consequence of the event.

Any new SAE that occurs after the study period and is considered to be related (possibly/probably) to the IP or study participation should be recorded and reported immediately.

A **life-threatening** adverse drug experience is any AE that places the patient, in the view of the investigator, at immediate risk of death from the reaction as it occurred, i.e., it does not include a reaction that, had it occurred in a more severe form, might have caused death.

